7.8. Mechanistic sub-study analysis

Extending the table in section 3.9 of the protocol, the planned analysis for the mechanistic sub-study endpoints are in table below. Since the distribution of all the variables is not clearly defined *a priori*, and the size of the subsample is relatively small, the statistical methods used at final analysis may not be exactly the same as the ones described. For example, a log-transformation may be needed, or a non-parametric method of analysis (such as Mann-Whitney test of the change score, or of the final score if less variable). Bootstrap 95% confidence intervals may also need to be computed.

Me obj	chanistic sub-study jectives:	Variables	Main summary statistic	Statistical method for comparison between arms and inference type
a.	To compare changes in colonic metabolism to identify the relative abundance of the bacterial	-Gut microbiota abundance (stool sample)	Means(SD)/Medians(IQR) of the AUC and/or the change over time in the AUC	ANCOVA with 95% CI
	component of the microbiome	-Hydrogen breath test (ppm)	Means(SD)/Medians(IQR) of the AUC and/or the change over time in the AUC	ANCOVA with 95% CI
b.	(i) To analyse the metabolite profile	Level of SCFA and metabolites profile (stool sample)	Means(SD)/ Medians(IQR)	ANCOVA, with 95% CI
	(ii) To determine how these specific changes in the colonic environment influence L-cell differentiation	Proliferation of L-cells in intestinal organoid	Means(SD)/ Medians(IQR)	ANCOVA, with 95% CI

iP	R	F١	V	F	N	Т

c.	Appetite regulation: (i) To compare subjective feelings of appetite	-Visual Analogue Scales (VAS) of appetite (4 scales: hunger; desire to eat; fullness; nausea)	Means(SD) or Medians(IQR) of the AUC or the change over time in the AUC	ANCOVA, with 95% CI
	(11) To compare anorectic gut hormones	- PYY - GLP-1	Means(SD) or	with 95% CI
		- Gastrin - CCK	Medians(IQR) of the AUC and/or of the change over time in the AUC	
d.	Mechanisms involved in weight maintenance:			
	(i)To compare energy expenditure	 Energy expenditure (kcal/day) Carbohydrate oxidation (g/min) Fat oxidation (g/min) RER (respiratory exchange ratio) 	Means(SD) or Medians(IQR) of the AUC and/or of the change over time in the AUC	ANCOVA with 95% CI
	(ii) To compare hepatic lipid metabolism	-Stable isotope tracers of fat oxidation (13CO2 + 13C-beta- hydroxybutyrate) -De Novo Lipogenesis (² H ₂ O)	Means(SD)/ Medians(IQR)	ANCOVA with 95% CI
	(iii) To compare Total Body			ANCOVA with
	Water	$-{}^{2}\text{H}_{2}\text{O}$ in body water	Means(SD)/Medians(IQR)	95% CI

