For the mechanistic studies, 34 volunteers (17 per group) would provide sufficient statistical power to detect a 15 pmol/L effect size in GLP-1 concentrations between groups, with 90% power, 5% significance value, SD 13 pmol/L. These differences are based on our previous published findings that report enhanced gut hormone release following IPE supplementation (13, 14). We therefore planned to recruit a subsample of **52 volunteers (26 per group)** to allow a 70% retention rate.

Sample size calculations were performed using nQuery Advisor 4.0 software and independently validated using Stata software.

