7.10. Handling multiple comparisons

Significance tests will be used sparingly and restricted where possible to addressing stated hypotheses. Secondary outcomes, as well as the primary outcome, will be summarised using an effect size with a 95% confidence interval. Interpretation for those secondary outcomes that do not directly address the stated study hypotheses will be more cautious. Where multiple outcomes address an objective, the interpretation will account for the role of the outcome within the objective and the strength and direction of effects in all outcomes.

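### Section 7.8's example rank fallback lets the data choose between change and final score and uses the baseline less efficiently than a baseline-adjusted rank test; the cost is a modest loss of power

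*SAP*

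**What the plan says.** The table in SAP section 7.8 plans "ANCOVA with 95% CI" for the sub-study endpoints. The text above it warns that, because the distributions are not known and the subsample is small, "the statistical methods used at final analysis may not be exactly the same as the ones described". It then gives examples, in this order: a log transformation; a non-parametric method, illustrated by a "Mann-Whitney test of the change score, or of the final score if less variable"; and the note that "Bootstrap 95% confidence intervals may also need to be computed". It does not say whether variability is judged within arm or overall, on blinded or unblinded data, or at what point.

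Related text elsewhere in the SAP:

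- Section 7.1, on data transformation, expects the need for transformation mainly in this sub-study.
- Section 6.6 lists the sub-study outcomes as changes from baseline at 12 months, and section 5.3.2 confirms that baseline is measured.
- Section 7.10 says that secondary outcomes, like the primary, "will be summarised using an effect size with a 95% confidence interval".
- Section 1.1 allows some analysis decisions to be taken late, possibly after unblinding. Section 4.7 has the sub-study analysed after the main report.

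**The concern.** For the primary outcome, section 7.2.1 treats change and 12-month value as interchangeable because the model adjusts linearly for baseline. A Mann-Whitney test has no such adjustment, so change and final score become two different comparisons. Under the example rule, the choice between them would be made outcome by outcome from the observed spread, and some outcomes could be reported on one scale and some on the other.

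The rule also gives up efficiency. The final score ignores baseline. The change score uses it by subtraction, which fixes the slope at 1 instead of estimating it. The sub-study expects only about 36 people at 12 months, so the baseline is useful information that has already been collected. A Mann-Whitney test also gives no baseline-adjusted effect, whereas the tabulated ANCOVA does.

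**Working it through.** **1. The SAP's own sub-study figure.** Section 4.5 states that "34 volunteers (17 per group) would provide sufficient statistical power". The inputs there are a GLP-1 difference of 15 pmol/L, an SD of 13 pmol/L, a 5% level (taken as two-sided) and 90% power.

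- Standardised effect: 15/13 = 1.15.
- Normal approximation: n per arm = 2(1.960 + 1.282)²/1.154² = 15.8, so 16.
- Exact two-sample t calculation: 17 per arm (power 90.3%); at 18 per arm, 92.0%.
- Expected at 12 months: 52 × 0.70 = 36.4, matching the 36 (18 per arm) in the section 7.1.5 flow diagram.

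The figure reproduces.

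**2. Why baseline adjustment helps, and where.** Suppose equal variance σ² at baseline and 12 months, with correlation ρ. The variance relevant to the arm comparison is σ² for the final score, 2(1 − ρ)σ² for the change score and (1 − ρ²)σ² for ANCOVA.

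| ρ | Final | Change | ANCOVA |
|---|---|---|---|
| 0 | 1.00 | 2.00 | 1.00 |
| 0.3 | 1.00 | 1.40 | 0.91 |
| 0.5 | 1.00 | 1.00 | 0.75 |
| 0.7 | 1.00 | 0.60 | 0.51 |
| 0.8 | 1.00 | 0.40 | 0.36 |

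Choosing the less variable score leads to the final score at low ρ and the change score at high ρ. The gap to ANCOVA is therefore largest near ρ = 0.5 and closes at both ends.

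**3. Power at the SAP's effect.** Simulation with 18 per arm, normal data, effect 1.15 SD, 40,000 trials per setting. Rank ANCOVA regresses the ranked 12-month value on arm and ranked baseline. The example rule is shown with spread judged within arm and overall.

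| ρ (assumed) | Rule, within-arm SD | Rule, overall SD | Rank ANCOVA | Gain (points) |
|---|---|---|---|---|
| 0.3 | 89.9% | 87.6% | 92.0% | 2.1 to 4.4 |
| 0.5 | 92.1% | 89.0% | 95.7% | 3.6 to 6.7 |
| 0.6 | 95.3% | 93.0% | 97.6% | 2.3 to 4.6 |
| 0.8 | 99.9% | 99.6% | 99.9% | 0 to 0.3 |

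For log-normal data (log-SD 0.8) at ρ = 0.5 the figures are 92.7% and 91.5% against 95.6%, a gain of 2.9 to 4.1. At ρ = 0.7 they are 98.4% and 97.8% against 99.2%, a gain of 0.8 to 1.4. Quade's test gave almost the same power as rank ANCOVA throughout.

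**4. Power at a smaller, assumed effect of 0.9 SD.** Log-normal data, ρ = 0.3/0.5/0.7:

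- rule with overall SD: 69/73/88%
- rule with within-arm SD: 71/75/89%
- rank ANCOVA: 75/82/92%

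The gain is 6/9/4 points against the overall rule and 4/7/3 against the within-arm rule. With normal data the gain runs from about 2 points (ρ = 0.7, within-arm: 90.6% against 92.6%) to 11.7 (ρ = 0.5, overall: 70.3% against 82.0%). Zero-inflated and heavy-tailed data, where a log transformation would not help, also showed a gain.

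**5. Type I error.** With no effect, ρ = 0.5 and normal data, the rule rejects in 5.9% of trials if spread is judged within arm and 4.7% if judged overall. For log-normal data the figures are 5.2% and 4.6%. Rank ANCOVA is at about 5%.

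**The case against.** Much of the case on the other side stands.

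- **The Mann-Whitney test is only an example.** It follows the words introducing an illustration, comes after log transformation, and does not exclude a baseline-adjusted rank test. A reader might infer that the SAP has fixed it as the fallback, or that it will probably be used. The text supports neither: the transformation text in section 7.1 predicts transformation and otherwise mentions bootstrap intervals.
- **For plainly skewed data the first-named remedy is better than either rank option.** With log-normal data at 0.9 SD, ANCOVA on the log scale has 78/85/95% power at ρ = 0.3/0.5/0.7, against 75/82/93% for rank ANCOVA in the same run. The point matters only where transformation does not solve the problem.
- **Baseline is not simply discarded.** A reader might infer that it is, but that is true only of the final score. The change score uses it, and the rule tends to select the change score when ρ is high.
- **A data-driven choice suggests inflated error.** Reporting whichever of the two tests had the smaller p-value would reject in about 8.5 to 9% of null trials, but the SAP does not propose that. Choosing by spread keeps the error near 5%.
- **Tests carry limited weight here.** The sub-study aims are exploratory, section 7.10 restricts significance testing, and section 7.8 already allows bootstrap intervals, so the SAP does not leave these outcomes without an interval.

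What this leaves untouched is that the example selects the score from the data without saying how or when, and that a method using the same collected data does as well or better over most of the plausible range.

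**Conclusion.** The point holds as a low-cost improvement. With 18 per arm and assumed ρ of 0.3 to 0.7, the example rule loses about 0 to 6 points of power at the SAP's 1.15 SD effect (6.7 at worst) and about 2 to 11 points at an assumed 0.9 SD (11.7 at worst). The loss is about nil at ρ = 0 and at ρ of 0.8 or above. At the SAP's own effect the rule still has about 88% power or more, so the documents do not support a claim that the sub-study is left badly underpowered. Nor do they support a claim of material false-positive inflation.

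The size rests on ρ, the 0.9 SD effect, the distribution shapes and equal variance at the two visits, none of which the SAP gives. The primary analysis is unaffected.

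**What to change.** In section 7.8:

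1. Keep ANCOVA on the log scale as the first remedy for skewness.
2. Where a rank method is still needed, replace the Mann-Whitney wording with one fixed baseline-adjusted rank test of the 12-month value, either rank ANCOVA or Quade's test. State that the need for it is judged on blinded, pooled data.
3. Report the baseline-adjusted ANCOVA difference with its bootstrap 95% interval as the main result. Label the rank test as supporting, because it targets a different quantity from a mean difference and the two can disagree on skewed data.

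The cost is about one sentence in the SAP and negligible extra analysis. No additional data are needed.

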7.9. Interim Analysis

As described in the DMEC charter, formal interim analysis of the primary outcome for early stopping is not planned for this study. Regular interim reports will be prepared for DMEC meetings every 6 to 12 months. There will be a stop-go decision on the recruitment which will not involve any interim analysis of the primary outcome (described in study protocol).

7.10. Handling multiple comparisons

Significance tests will be used sparingly and restricted where possible to addressing stated hypotheses. Secondary outcomes, as well as the primary outcome, will be summarised using an effect size with a 95% confidence interval. Interpretation for those secondary outcomes that do not directly address the stated study hypotheses will be more cautious. Where multiple outcomes address an objective, the interpretation will account for the role of the outcome within the objective and the strength and direction of effects in all outcomes.

7.11. Handling protocol deviations

The number (percentage) and type (major/minor) of protocol deviations with potential to affect the primary outcome of the trial will be summarized by treatment group. No formal statistical test comparing the groups will be undertaken as it is not expected for this to happen in many patients. Nevertheless, if there are at least 5% of study subjects that were unblinded during the study or were known to have taken part in a weight loss program or consumed a weight loss product then a sensitivity analysis removing these subjects from the primary statistical model will be carried out to assess robustness of the results.

7.12. Software

The principal statistical software package will be IBM SPSS Statistics 25, and R software will be available if required.

8. IMPACT OF COVID-19

8.1. On data quality and usage of data

The possibility of subjects having COVID-19 was already addressed in tables 7.2.2 and 7.7.

As written in the iPREVENT guidance document of COVID-19 restrictions, all in-person clinic study visits have been suspended until further notice, with follow up visits being conducted only remotely. This means that body weight (primary outcome) will be self-reported during the restriction time.

When subjects return to clinic study visits, these will be asked to measure their weight before going into the clinic so that the self-reported weight can be compared with the weight measured at the clinic using the Bland and Altman limits of agreement and correlations. Since the self-reported weight was collected at the pre-screening questionnaire it is possible to measure change in measured weight and self-reported weight. These will be discussed with independent committees.

Since it is hoped that all subjects reach the 12-month visit in a non-restricted/covid-19 period, only the weight measured at the clinic will be considered for the primary outcome of the trial.

8.2. On model assumptions not being met

In the eventuality of low recruitment, or the trial having to stop early due to COVID pandemic or high dropout, the sample size may be smaller than expected. Also, the model may be over-parameterised. In these situations, the model may not converge. In this eventuality, the reason for the non-convergence will be explored. It may be due to the covariance structure and/or too many fixed-effect parameters. The non-convergence may disappear after simplifying the covariance structure (to being distinct variances per timepoint but a common correlation) and/or by removing the interactions of time with all fixed effects except for arm and baseline (and missing indicator if needed) – the "reduced set" of covariates. If only one of these two actions were necessary, then we would prefer to retain the complex covariance structure. If neither action removed the non-convergence, ANCOVA models would be fitted for each timepoint, involving ideally all planned fixed-effects, or otherwise the "reduced set". The same model was fitted successfully in a previous trial that had more arms and timepoints, and similar sample size per arm (25). If any these situations occur, we will check which of these several options are feasible just before database lock.

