4.2. Treatment Groups

The trial is randomised with two arms and with equal allocation of participants in a 1:1 ratio to these arms. **Active Arm**: IPE for 12 months; **Placebo Arm**: Inulin for 12 months.

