4.5. Sample Size

On the basis outlined below, a sample size of 270 randomised participants (135 per arm) was chosen to provide 90% power to detect a 2kg difference between arms in mean body weight change over 12 months using a two-sided 5% significance test, assuming a 4.35kg SD and with 25% dropout allowance.

Determination of the primary outcome effect size:

In the randomised proof of concept trial, the difference between arms in the change in body weight over 24 weeks was 1.4kg (95% CI: -0.3 to 3.1), p=0.099. Using a Bayesian method recommended for preliminary trials in which evidence in the 95% CI is translated into probabilities, there was a 95% posterior probability of an underlying positive between-arm difference favouring the intervention (11). The posterior probability of intervention-favouring differences greater than 1kg, than 1.5kg, and 2kg were respectively 69%, 47% and 25% based on 24-week intervention. The difference increased in magnitude through successive 8-week, 16-week, and 24-week timepoints. By 24 weeks there were significant reductions in the proportion of intervention participants gaining \geq 3%, and \geq 5% of body weight from a mean baseline of 90kg. We therefore chose a 2kg between-arm 12-month effect size.

Determination of the primary outcome variability:

The chosen detectable effect size of 2kg agreed with that in a weight gain prevention trial conducted over 9 months in young adults (12) by also aiming to detect a 2kg effect, and achieved 4.3kg with 81% retention. The pooled standard deviation (SD) for body weight change was 4.35kg.

Power to detect the effect:

We set a 90% power to detect the primary outcome effect size of 2kg.

Determination of the sample size based on the primary outcome:

The sample size was set to be **270 participants, 135 per arm**. This involves a 25% allowance loss of 12-month primary outcomes, and two-sided statistical testing at the 5% significance level, implying that 202 subjects are required to be followed up with a valid primary outcome. Further adjustment for baseline body weight is expected to improve the precision of the estimated treatment effect.

Power calculation for Mechanistic outcomes:

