7.2. Primary outcome analysis

7.2.1 Description

be included.

The primary outcome measure is the change from baseline in body weight at 12 months. As the analysis approach for continuous outcomes below makes advantage of linear covariate-adjustment for the baseline of the outcome, the primary endpoint can equivalently be regarded to be each participant's 12-month measurement. This is convenient because then those with a 12- month outcome, but whose baseline measurement is missing, are not regarded to be missing the endpoint. The primary outcome is therefore operationalised within the statistical model as the 12-month body weight, rather than the change in this from baseline to 12 months. It is not thought that this outcome will be missing at baseline, as it is involved in eligibility criteria and is a minimisation factor. This approach may be more useful for other outcomes. The primary outcome will be analysed using a repeated measures ANCOVA via a linear mixed effects (LME) model incorporating the 3 post-baseline measurements of the body weight (2, 6 and 12 months). All outcome measurement from all randomised subjects who provide at least one post-baseline valid measurement will

This mixed model will include fixed effect terms for arm (1 parameter), centre (1 parameter), sex (1 parameter), age (1 linear parameter), BMI within ethnicity (3 parameters), whether or not subjects volunteer to take part in the sub study (1 parameter), "time" (2 parameters), the baseline of the outcome (continuous body weight -1 parameter) and its missing indicator required for the missing indicator method (1 parameter , if needed) (20). Additionally, the model will include a fixed effect to indicate whether the primary outcome was measured by the participant at each timepoint. The other effects to be included in the model will be the interactions between "time" and each of the other fixed effects in the model (20 parameters). This model allows the treatment effect to be formally tested, at the primary timepoint of 12 months, and estimated at 2 and 6 months. Age is included because this was found to predict drop-out in a related trial (21).

Models will be fitted using a restricted maximum likelihood estimation using an unstructured variancecovariance matrix for the within-subject residuals (since there are only three follow-up timepoints, and so there is a manageable enough number of covariance parameters to expect this type of matrix to be supported by the sample size).

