7.2.3 Missing data

An expert missing-data group concluded that rather than statisticians reacting to missing data at the end of a trial, there should be comprehensive, proactive planning for handling missing data at the stage of designing trials (22). The group recommended there should be consideration of missing data mechanisms (e.g Missing At Random), and, if the missing data may be informative that appropriate sensitivity analyses should be undertaken to investigate the robustness of the inferences to the different assumptions made by the main analysis.

It is anticipated that there may be approximately 25% missing data at the 12-month timepoint. The linear mixed effects model, above, will assume that the missing data is "missing at random" (MAR). This is an advantage over the assumption that the missing data is "missing completely at random" because it corrects for contribution to missing data from the covariates in the model and the correlated body weight outcome over time. The robustness to this assumption will be challenged using the sensitivity analyses. Multiple imputation is an alternative approach that also makes a MAR assumption, however we will use the likelihood approach of the linear mixed effects model, above, that gives similar resulting estimates (23).

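### The last-resort ANCOVA in SAP 8.2 has no missing-data provision, so the 12-month estimate would ignore the 2- and 6-month weights of participants without a 12-month weight

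*SAP*

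**What the plan says.** SAP 7.2.1 fits a linear mixed model to the 2-, 6- and 12-month weights. It takes data "from all randomised subjects who provide at least one post-baseline valid measurement".

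SAP 7.2.3 expects about 25% of 12-month weights to be missing and assumes they are missing at random. It prefers this to a stricter assumption because "it corrects for contribution to missing data from the covariates in the model and the correlated body weight outcome over time". It names multiple imputation as an alternative that makes the same assumption and gives similar estimates, and chooses the likelihood approach.

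SAP 7.2.2 discards weights recorded after a known pregnancy and relies on the mixed model to stand in for them.

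SAP 8.2 deals with non-convergence, which it links to low recruitment, early stopping or high dropout. The cause is explored first. Then the covariance is simplified, or most time interactions are removed, or both. Only then: "If neither action removed the non-convergence, ANCOVA models would be fitted for each timepoint, involving ideally all planned fixed-effects", or otherwise a smaller covariate set. Nothing is said about missing 12-month weights at this step.

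**The concern.** An ANCOVA fitted at 12 months alone can use only participants who have a 12-month weight. Someone weighed at 2 and 6 months and then lost counts in the 7.2.1 analysis but not in this one. The part of the 7.2.3 assumption that rests on the serial weights goes with them. Women whose later weights are removed after pregnancy would also leave the 12-month comparison, instead of contributing through their earlier weights.

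The change is not acknowledged in 8.2, and high dropout and early stopping are situations in which more participants have early weights and no 12-month weight. The tipping-point shifts in 7.2.4 are defined on the mixed-model estimate and are not restated for an ANCOVA. At stake is bias in the primary estimate if dropout is related to earlier weight differently in the two arms.

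**Working it through.** **The plan's own figures.** Inputs from SAP 4.2 and 4.5: difference 2 kg ("We therefore chose a 2kg between-arm 12-month effect size"), SD 4.35 kg ("The pooled standard deviation (SD) for body weight change was 4.35kg"), "two-sided statistical testing at the 5% significance level", power 90% ("We set a 90% power to detect the primary outcome effect size of 2kg"), and "equal allocation of participants in a 1:1 ratio to these arms".

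- n per arm = 2 × 4.35² × (1.960 + 1.282)² / 2² = 99.4, so 100. With the t distribution, 101 per arm gives 90.2%, so 202 in total.
- Inflation for 25% loss: 200 / 0.75 = 267, against 270 stated. 270 × 0.75 = 202.5, against 202 stated.

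Both figures reproduce.

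**Who is left out.** 270 − 202 = 68 participants have no 12-month weight. Those among them with a 2- or 6-month weight are in the 7.2.1 analysis but not in the 12-month ANCOVA. The SAP does not say how many that would be. Anyone with no post-baseline weight contributes to neither.

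**Power.** The trial was sized on participants with a 12-month weight, so the fallback keeps the design power: 90.4% with 202 analysed (normal approximation). It is 88.3% at 30% missing (188 analysed) and 83.3% at 40% (162).

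**Bias.** Not in the SAP and therefore assumed:

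- 6-month SD of 3.2 kg, and a correlation r between 6- and 12-month weight change of 0.6 to 0.85;
- all dropout falls after the 6-month visit, with log-odds rising by b = 0.15 to 0.35 per kg of 6-month gain;
- 25% missing, true effect −2.0 kg, no further covariate adjustment.

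Let z be standardised 6-month change and p(z) = 1/(1 + exp(−(a + 3.2bz))), with a set so that the mean of p is 0.25. Among completers, the mean of z is z̄ = E[z(1 − p)] / E[1 − p]. By numerical integration z̄ = −0.115 at b = 0.15 and −0.231 at b = 0.35. The completers' 12-month mean in that arm is off by r × 4.35 × z̄.

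- Smallest case: 0.6 × 4.35 × 0.115 = 0.30 kg.
- Largest case: 0.85 × 4.35 × 0.231 = 0.85 kg.

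| r | b per kg | Control arm only | IPE arm only | Both arms equally |
|---|---|---|---|---|
| 0.6 | 0.15 | −1.70 | −2.30 | −1.97 |
| 0.6 | 0.35 | −1.40 | −2.60 | −1.88 |
| 0.85 | 0.15 | −1.57 | −2.43 | −1.96 |
| 0.85 | 0.35 | −1.15 | −2.85 | −1.83 |

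Entries are the completers' estimate in kg. The last column uses one dropout rule for both arms, 25% missing overall, and a 6-month mean 1 kg lower on IPE (assumed). If each arm loses exactly 25% under the same slope, the two errors cancel and the bias is zero.

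**Using the earlier weight.** Regression on 6-month weight has slope r × 4.35 / 3.2. Completers differ from the whole arm by 3.2 × z̄ at 6 months. The correction is therefore −r × 4.35 × z̄, which cancels the error and returns −2.0 kg. Simulation of the same comparison gave estimates within about 0.03 kg of −2.0.

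**Scale.** The standard error with 101 per arm is 4.35 × √(2/101) = 0.61 kg, so the one-arm biases are about 0.5 to 1.4 standard errors.

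**The case against.** The strongest reply is that this is a remote contingency. A reader might infer that any non-convergence sends the primary analysis to ANCOVA. Section 8.2 does not say that: the simplifications before it, alone or together, remain mixed models and keep the likelihood handling of missing weights. The SAP also reports that the same model was fitted successfully in a trial with more arms and timepoints and a similar size per arm. That stands.

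A reader might also infer that the missing-at-random assumption is lost. It is narrowed. ANCOVA remains valid if missingness depends only on arm and the planned baseline covariates, which include age because age predicted dropout in a related trial.

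Nor does the estimand change. Section 7.2.2 still fixes the population, endpoint, strategies and summary measure; the fallback is a different estimator of the same quantity under a stronger assumption.

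Section 7.2.4 might be read as predicting dropout driven by early weight gain. It offers lack of improvement as one example among reasons that may be unknown, allows departures in either direction, and does not say that dropout reasons will differ by arm.

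Finally, the tipping-point analysis already shifts the estimate by up to 0.25 × 5 = 1.25 kg at 25% missing in the affected arm, more than the largest bias above. Its additive shift carries over to an ANCOVA estimate. That is fair, but it explores departures from the primary assumption. It does not recover information from earlier weights that have already been collected.

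**Conclusion.** The point holds for the final step of 8.2 only. As written, that step sets aside the 7.2.1 inclusion rule, drops the serial-weight part of the 7.2.3 assumption, and leaves the pregnancy handling in 7.2.2 without its model.

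The consequence is possible bias, in either direction: about 0.3 to 0.85 kg if dropout depends on 6-month weight in one arm only, and about 0 to 0.2 kg if it does so equally in both. These sizes are illustrative. They rest on an assumed 6-month SD, correlation and dropout slopes, and on all dropout falling after a 6-month weight, which favours a method that uses that weight.

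A reader might expect lost power as well. The documents do not support that, since the sample size already counts only participants with a 12-month outcome. Because the step is unlikely to be reached, this is an inexpensive improvement to a contingency rule and not a flaw in the planned primary analysis.

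**What to change.** Keep the order of steps in 8.2 and change only the last. Suggested content:

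- If neither simplification, alone or combined, achieves convergence, multiply impute the 12-month weight separately within each arm, using the 2- and 6-month weights and the planned covariates. Weights removed after pregnancy are treated as missing and imputed in the same way.
- Fit the 12-month ANCOVA with the planned fixed effects to each imputed dataset and combine the results by Rubin's rules.
- State that the three tipping-point scenarios in 7.2.4 are then applied to this combined estimate.

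This uses a method that 7.2.3 already describes as sharing the primary assumption and giving similar estimates. The cost is a few sentences of SAP text before database lock, and a little extra programming only if the fallback is used.
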